9. PRE-STUDY AND CONCOMITANT INTERVENTION/MEDICATION

Concomitant medications will be documented during screening and updated during the study. Disallowed concomitant interventions for this study include ocular medications of any kind, or any systemic medications that would normally contraindicate contact lens wear or may otherwise compromise study endpoints.

9.1. Systemic Medications

Certain systemic medications are known to have a higher likelihood to interfere with contact lens wear, chiefly by disrupting the tear film.

A summary of disallowed systemic medications is shown in . Subjects with a history of taking these medications will be allowed to enroll only if:

- The medications have been taken on a continual, routine basis for at least 6 months, and
- The subject has demonstrated successful contact lens wear during this time.

Or:

- The subject was taking the medication on a temporary basis and ceased taking that medication at least 2 weeks prior to signing the informed consent (this is considered sufficient time for the medication to have left the body prior to enrollment).

Subjects with a history of taking medications listed in on a long-term, routine basis for less than 6 months will not be allowed to participate in the study.

Table 4: Disallowed systemic medications

Class of Drug	Common Indication(s)	Common Examples
Estrogens (not including contraceptive medication)	Menopause, osteoporosis, vaginitis	Vagifem, Estrace, Climara, Vivelle-Dot, Premarin, Minivelle, etc.
Anticholinergics	Irritable bowel syndrome, Parkinson's disease, peptic ulcer, cystitis, nasal congestion, cold symptoms, overactive bladder, COPD	Bentyl, Spiriva, Atrovent, Hyosyne, Levsin, Symax Fastab, Symax SL, Homax SL, Cogentin, Transderm Scop, etc.
Beta-blockers	Hypertension, angina, heart attack, migraine, atrial fibrillation, adrenal cancer, essential tumor, glaucoma	Toprol XL, Lopressor, Tenormin, Propranolol, Timoptic, Trandate, Inderal LA, etc.
Psychotropics	Antipsychotic (schizophrenia, mania), antidepressant, antiobsessive, antianxiety, mood stabilizer, stimulants (ADHD)	Zoloft, Celexa, Prozac, Lexapro, Effexor, Cymbalta, Ativan, Xanax, Desyrel, Wellbutrin, etc.
Vitamin A analogs	Cystic acne	Isotretinoin

Examples of disallowed systemic antihistamines are given in . Subjects with a history of taking systemic antihistamines will be allowed to enroll only if:

- They have taken antihistamines continuously for at least 2 weeks, and
- They have demonstrated successful wear while taking the medication

Or:

- They stopped taking the medication for at least 2 weeks prior to enrollment.

Clinical Study Protocol
Johnson & Johnson Vision Care, Inc.

Table 5: Disallowed systemic antihistamines

Class of Drug	Common Indication(s)	Common Examples
Antihistamines	Allergic rhinitis, sedation, hives, allergic conjunctivitis, skin allergy, itching, motion sickness	Hydroxyzine, Promethazine, Phenadot, Vistaril, Claritin, Zyrtec, Astepro, Astelin, Optivar, Allegra, Benadryl, etc.

10. DEVIATIONS FROM THE PROTOCOL

Investigator will notify study sponsor upon identification of a protocol deviation. Protocol deviations must be reported to the sponsor within 24 hours after discovery of the protocol deviation. The Investigator will report deviations per IRB/IEC requirements. All deviations will be tracked, and corrective actions implemented as appropriate.

If it becomes necessary for the Investigator to implement a deviation in order to eliminate an immediate hazard to the trial subject, the Investigator may implement the deviation immediately without notification to the sponsor. Within 24 hours after the implemented deviation, the Investigator must notify and provide the rationale to the Sponsor and, as required, to the IEC/IRB.

If the deviation potentially impacts the safety of subject or changes the technical integrity of the study, then it must be reported to IEC/IRB. This is a "Major Deviation". Deviations that contradict the information contained in the Informed Consent/Assent forms will be considered Major Deviations.

Minor deviations have no substantive effect on subject safety or technical integrity of the study. They are often logistical in nature.

Protocol waivers are prohibited.

lists examples of deviations that will constitute major and minor protocol deviations for this study.

Table 6: Examples of major and minor protocol deviations

Deviation category	Major deviation	Minor deviation
Out-of-window visit (applies to wear periods only, i.e. not washout period)	Visit attended > 2 days out of visit window defined in study procedures	Visit attended ≤ 2 days out of visit window defined in study procedures

In the case of a major protocol deviation, the decision of whether or not the subject will be excluded from the Per-Protocol analysis population will be made at the time of cohort review. The list of major deviations with potential impact on the primary endpoint will be flagged separately and used to define the per protocol population.

11. STUDY TERMINATION

If more than 2 subjects in the investigational soft contact lens group develop serious expected (e.g., definite or probable MK) or unexpected device related adverse events, the study will be suspended. Upon review and consultation with IRB, DMC, and JJVC Safety Management Team, the study may be terminated. This potential stopping rule is established based on our trial involving approximately 200 subjects wearing the investigational soft contact lens for up to 3 years with an assumed MK rate that is below 0.2% per subject-year. The rate of 0.2% per subject-year is the established rate for extended wear lenses in adults, which was requested by the FDA as a criterion for evaluating a contact lens for pediatric use in an FDA response to a pre-IDE submission. To be conservative, 200 independent subject years were used in the calculation. The probability of observing 2 cases or

Clinical Study Protocol
Johnson & Johnson Vision Care, Inc.

more incidents of MK is 0.061, and 3 cases or more incidents of MK is 0.007 (given an MK rate of 0.2% per subject year).

The occurrence of one or more Unanticipated Serious Adverse Device Effect (USADE), or any SAE where the relationship to study agent cannot be ruled out, may result in stopping further dispensing of test article. In the event of a USADE or SAE, the Sponsor may unmask the treatment regimen for the subject(s) and will discuss this with the Investigator before any further subjects are enrolled.

The Sponsor will determine when a study will be stopped. The Principal Investigator always has the discretion to initiate stopping the study based on subject safety or if information indicates the study's results are compromised.

JJVC reserves the right to terminate the study at any time for any reason and will follow the internal applicable quality review process and will notify the IEC/IRB. Additionally, the IEC/IRB reserves the right to terminate the study if an unreasonable risk is determined. The study can be terminated by the Principal Investigator at the individual clinical site due to specific clinical observations, if in their opinion, after a discussion with JJVC, it is determined that it would be unwise to continue at the clinical site.

JJVC (and the IEC/IRB and DMC, if applicable) will evaluate all adverse events. If it is determined that an adverse event presents an unreasonable risk, the investigation, or that part of the investigation presenting the risk, will be terminated as soon as possible.

Should the study be terminated (either prematurely or as scheduled), the Investigator will notify the IEC/IRB and Regulatory Authority as required by local regulatory requirements.

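### The suspension rule in Section 11, paragraph 1, is carried over from a trial of about 200 subjects over up to 3 years and has no valid basis in this two-visit study of about 7 subjects

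*Combined protocol and SAP*

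**What the plan says.** Section 11, paragraph 1, sets a count and a consequence: "If more than 2 subjects in the investigational soft contact lens group develop serious expected" (with definite or probable MK as the example) "or unexpected device related adverse events, the study will be suspended". It then adds: "Upon review and consultation with IRB, DMC, and JJVC Safety Management Team, the study may be terminated".

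The count is justified by outside material. The potential "stopping rule is established based on our trial involving approximately 200 subjects wearing the investigational soft contact lens for up to 3 years". On the rate: "The rate of 0.2% per subject-year is the established rate for extended wear lenses in adults", which the text says the FDA had asked for as a criterion when a lens is evaluated for pediatric use. On exposure: "To be conservative, 200 independent subject years were used in the calculation". On the result: the probability of 2 cases or "more incidents of MK is 0.061, and 3 cases or more incidents of MK is 0.007".

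Paragraph 2 deals with single events. One unanticipated serious adverse device effect (USADE), or one serious adverse event (SAE) whose relationship cannot be excluded, "may result in stopping further dispensing of test article". After such an event the sponsor is to discuss it with the investigator before enrolment goes on.

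The rest of the protocol describes a different study:

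- **Size and duration.** About 7 enrolled and at least 5 completing, over about 6 weeks (Section 4.3); about 1 week per subject (Synopsis, Study Duration).
- **Population.** Adults aged 18 to 39 (Section 3.1). Current extended-wear users are excluded (Section 3.3).
- **Exposure.** Daily wear (Synopsis), in the office only (Section 6.3).
- **Products and design.** No investigational product; two marketed lenses (Synopsis). Every subject is assigned both in a 2×2 crossover (Section 4.1).
- **Oversight.** Section 16.4 marks the DMC as not applicable.

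**The concern.** A stopping threshold is only as good as the exposure and event rate behind it. Paragraph 1 takes both from elsewhere, so the reason given for the number 3 does not carry over. An ethics committee reading Section 11 would see a threshold that appears to have a statistical justification, when for this study it has none.

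Two of the rule's terms also lack a counterpart here. There is no investigational lens, and in a crossover there is no separate lens group. The committee named for the termination step has not been set up.

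This matters because paragraph 1 is the only count-based mandatory suspension in the protocol. Read literally, nearly half of the enrolled subjects must have a qualifying event before it applies.

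**Working it through.** **1. Reproduce the plan's figures.** Inputs from Section 11: 200 subject-years and an MK rate of 0.002 per subject-year. With X ~ Binomial(200, 0.002):

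- P(0) = 0.998^200 = 0.67005
- P(1) = 200 × 0.002 × 0.998^199 = 0.26856
- P(2) = 19,900 × 0.002² × 0.998^198 = 0.05355
- P(X ≥ 2) = 1 − 0.67005 − 0.26856 = 0.0614 (plan: 0.061)
- P(X ≥ 3) = 0.0614 − 0.0536 = 0.0078 (plan: 0.007, which is this value truncated)

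A Poisson check with mean 0.4 gives 0.0616 and 0.0079. At 200 × 3 = 600 subject-years the binomial values would be 0.337 and 0.120. The quoted figures therefore belong to 200 subject-years.

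**2. Exposure in this study.** In-office wear time is not given in the visible text, so I bound it.

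- Ceiling, all 7 subjects exposed for the full 6 weeks: 7 × 42 / 365.25 = 0.805 subject-years.
- About 1 week each: 7 × 7 / 365.25 = 0.134 subject-years.

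Even the ceiling is smaller than the stated basis by a factor of 200 / 0.805 ≈ 248.

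**3. The same calculation at this study's size.** Keep the plan's rate of 0.002 and take the per-subject risk as p = 1 − exp(−expected cases / 7), with X ~ Binomial(7, p).

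| Exposure | Expected MK cases | P(at least 1) | P(at least 3) |
|---|---|---|---|
| 0.805 subject-years | 0.805 × 0.002 = 0.0016 | 0.0016 | 4.3 × 10⁻¹⁰ |
| 0.134 subject-years | 0.134 × 0.002 = 0.00027 | 0.00027 | 2.0 × 10⁻¹² |

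As a check at the ceiling: p ≈ 0.00023, and P(X ≥ 3) ≈ 35 × p³ ≈ 4.3 × 10⁻¹⁰.

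**4. What the count means as a share of subjects.** More than 2 means at least 3.

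- Stated basis: 3/200 = 1.5%
- Enrolment target here: 3/7 = 43%
- Completion target here: 3/5 = 60%

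**5. Can the rule be applied as worded?** If investigational is read as the Test lens, events can be counted by the lens actually received, as the Safety Population in Section 14.3 does. On that reading, events on the Control lens, which every subject is also assigned, do not count towards suspension. The DMC appears only in the sentence on termination; suspension itself does not depend on it. A later paragraph of Section 11 adds an if-applicable qualifier to the DMC, but paragraph 1 does not.

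**The case against.** The best defence is that this is leftover template text with little practical effect, and much of that stands.

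- **Single events are already covered.** Paragraph 2 allows a stop after one USADE or one possibly related SAE, and Section 11 says that the sponsor will discuss it with the investigator before further enrolment. (The parallel Synopsis entry on Study Termination says only that the sponsor may do so.)
- **Other routes exist.** Section 11 has all adverse events evaluated and requires termination if a risk is found unreasonable. The sponsor, the investigator and the ethics committee can each stop the study. Section 8.2 withdraws individual subjects for significant or serious events that require stopping lens wear.
- **The comparator is not ignored.** A note in Section 13.1 extends adverse device effects to a comparator device, and paragraph 2 and the later text of Section 11 are not limited to one lens.

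A reader might go further and infer that non-serious unexpected device-related events are left without protection. The documents do not support this firmly. In the paragraph 1 wording, serious may govern both expected and unexpected events. If it does, paragraph 2 already addresses each of these events at a count of one. Even on the wider reading, the evaluation of all adverse events still applies.

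A reader might also infer that suspension cannot work without a DMC. It can, because the DMC is named only for the later decision to terminate.

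None of this repairs paragraph 1. These routes limit the harm, but they do not give the 3-subject threshold a basis in this study, nor do they supply the lens group and committee that it names.

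**Conclusion.** The point holds as an error in the text of a decision rule. Paragraph 1 states a mandatory threshold whose sample size, duration, rate criterion, product and committee belong to another trial. The quoted 0.061 and 0.007 are right for 200 subject-years and say nothing about a study with at most 0.80. As it stands, the trigger needs 43% of the enrolment target. At the plan's own MK rate it would be met with probability of at most about 4 × 10⁻¹⁰.

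These figures assume 7 subjects (the plan says approximately) and a constant hazard at the extended-wear rate. The ceiling counts all 6 weeks as exposure, so in-office wear will give less. The mismatch itself depends on none of these assumptions.

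The consequence is limited. The documents do not show that subjects would go unprotected, or that the study needs any particular count for non-serious events. No endpoint or analysis relies on the paragraph. It should still be corrected, because it is operative text and the correction is cheap.

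**What to change.** Remove from paragraph 1 the 200-subject, 3-year basis, the extended-wear and pediatric MK criterion, the two probabilities and the DMC reference. Restate the trigger for this study, for example:

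*Lens fitting will be suspended, pending review by the sponsor's Safety Management Team and the IEC/IRB, if any 1 subject has a serious device-related adverse event on either AO1DfA or DT1fA.*

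Whether to add a count for non-serious unexpected device-related events is the sponsor's choice. If one is added, give a reason that fits about 7 subjects. Paragraph 2 can stay as it is.

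**Cost.** A one-paragraph protocol revision submitted to the IEC/IRB (Section 18.3), and a small chance of a temporary pause. For MK that chance is at most 0.16%, the ceiling P(at least 1) above. Section 13.1 lists other serious ocular events, such as iritis and uveitis, for which the documents give no rate, so their contribution cannot be calculated. No endpoint, sample size or analysis changes.

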12. PROCEDURE FOR HANDLING PRODUCT QUALITY COMPLAINTS

A Product Quality Complaint (PQC) refers to any written, electronic, or oral communication that alleges deficiencies related to the identity, quality, durability, reliability, safety, effectiveness, or performance of test articles after they have been released for clinical trial use.

Potential complaints may come from a variety of sources including but not limited to subjects, clinical research associates (CRA), clinical operations managers (COM), medical monitors, and site personnel, etc. The following are not considered product quality complaints:

- Subject satisfaction inquiries reported via "Subjective Questionnaires" and "Patient Reported Outcomes (PRO)."
- Clinical test articles that are stored improperly or damaged after receipt at the investigational site.
- Lens replacements that occur due to drops/fall-outs.
- Damage deemed by clinicians or clinical staff caused by handling by the user, and not indicative of a quality deficiency (i.e. tears, rips, etc.), only in situations where there is no deficiency alleged by the subject.

Within 24 hours of site personnel becoming aware that a PQC has occurred, the PQC must be recorded in the EDC system, which will trigger an automatic email notification to the appropriate COM/CRA and Clinical QA representative. In cases where the EDC system in use is not configured to send automatic notifications or when an EDC system is not used, the COM/CRA is responsible for notifying Clinical QA upon discovery that a PQC has occurred.

Upon receipt of the EDC notification, the COM/CRA will contact the study site to collect additional information which will include:

- Date the complaint was received/recorded in the EDC System (Date of Sponsor Awareness).
- Who received the complaint.
- Study number.
- Clinical site information (contact name, site ID, telephone number).
- Lot number(s).

Clinical Study Protocol
Johnson & Johnson Vision Care, Inc.

- Unique Subject Identifier(s).
- Indication of who first observed complaint (site personnel or subject).
- OD/OS indication, along with whether the lens was inserted.
- Any related AE number if applicable.
- Detailed complaint description (scheduled/unscheduled visit, wear time, symptoms, resolution of symptoms, etc.).
- Eye Care Provider objective (slit lamp) findings if applicable.
- Confirmation of product availability for return (and tracking information, if available), or rationale if product is not available for return

Once a complaint is received, it will be assessed by the COM, CRA, or trained site personnel to determine if it is an Adverse Event/Serious Adverse Event (AE/SAE). If the complaint results in an AE/SAE, the COM/CRA, or trained site personnel will follow section 13 of this protocol. If the AE/SAE was potentially the result of a product quality related deficiency, these procedures also apply and will be executed in parallel.

In some cases, a PQC form may be generated in EDC by the site in error. In this event, the PQC forms will be marked "Intentionally Left Blank" or "ILB". Justification for ILB must be documented.

13. ADVERSE EVENTS

13.1. Definitions and Classifications

Adverse Event (AE) – An AE is “any untoward medical occurrence, unintended disease or injury, or untoward clinical signs (including abnormal laboratory findings) in subjects, users or other persons, whether or not related to the investigational medical device and whether anticipated or unanticipated.”

NOTE: This definition includes events related to the investigational medical device or the comparator, and to the procedures involved. For users or other persons, this definition is restricted to events related to investigational medical devices.¹

An AE includes any condition (including a pre-existing condition) that:

1. Was not present prior to the study, but appeared or reappeared following initiation of the study.
2. Was present prior to the study but worsened during the study. This would include any condition resulting from concomitant illnesses, reactions to concomitant medications, or progression of disease states.

NOTE: Pregnancy must be documented as an adverse event and must be reported to the clinical monitor and to the Sponsor immediately upon learning of the event.

Serious Adverse Event (SAE) – An SAE is any adverse event that led to any of the following:

- Death
- Serious deterioration in the health of the subject that resulted in any of the following:
 - Life-threatening illness or injury
 - Permanent or persistent impairment of a body structure or a body function
 - Hospitalization or prolongation of patient hospitalization
 - Medical or surgical intervention to prevent life-threatening illness or injury or permanent impairment to a body structure or a body function.
 - Chronic disease
- Foetal distress, foetal death or a congenital physical or mental impairment of birth defect.

Diagnoses and conditions that are considered Ocular Serious Adverse Events include, but not limited to:

- Microbial Keratitis (MK)
- Iritis (including cells in the anterior chamber)
- Permanent decrease in best spectacle corrected visual acuity equivalent to 2 acuity lines or greater
- Central Corneal Opacity
- Central Corneal Neovascularization

Clinical Study Protocol
Johnson & Johnson Vision Care, Inc.

- Uveitis
- Endophthalmitis
- Hypopyon
- Hyphemia
- Penetration of Bowman's Membrane
- Persistent Epithelial Defect
- Limbal cell Damage leading to Conjunctivalization

Significant Adverse Events – are defined as events that are symptomatic and warrant discontinuation (temporary or permanent) of the contact lens wear

Diagnoses and conditions that are considered Ocular Significant Adverse Events include, but not limited to the following:

- Contact Lens Induced Peripheral Ulcer (CLPU)
- Significant Infiltrative Events (SIE)
- Superior Epithelial Arcuate Lesions (SEALS)
- Any Temporary Loss of > 2 Lines of BSCVA
- Other grade 3 or higher corneal findings, such as abrasions or edema
- Non-contact lens related corneal events - e.g. Epidemic Keratoconjunctivitis (EKC)
- Asymptomatic Corneal Scar
- Any corneal event which necessitates temporary lens discontinuation > 2 weeks

Non-Significant Adverse Events – are defined as those events that are usually asymptomatic and usually do not warrant discontinuation of contact lens wear but may cause a reduction in wear time. However, the Investigator may choose to prescribe treatment as a precautionary measure.

Diagnoses and conditions that are considered Ocular Non-Significant Adverse Events include, but not limited to the following:

- Non-significant Infiltrative Event (NSIE)
- Contact Lens Papillary Conjunctivitis (CLPC)
- Superficial Punctate Keratitis (SPK)
- Conjunctivitis: Bacterial, Viral, Allergic
- Blepharitis
- Meibomianitis
- Contact Dermatitis
- Localized Allergic Reactions
- Hordeolum
- Any corneal event not explicitly defined as serious or significant adverse event, which necessitates temporary lens discontinuation < 2 weeks

Adverse Device Effect (ADE) – An ADE is an “adverse event related to the use of an investigational medical device.”

NOTE 1: This definition includes adverse events resulting from insufficient or inadequate instructions for use, deployment, implantation, installation, or operation, or any malfunction of the investigational medical device.

NOTE 2: This definition includes any event resulting from use error or from intentional misuse of the investigational medical device.

NOTE 3: This includes ‘comparator’ if the comparator is a medical device.

Serious Adverse Device Effect (SADE) - Any adverse device effect that has resulted in any of the consequences characteristic of a serious adverse event.

Unanticipated Serious Adverse Device Effect (USADE): serious adverse device effect (SADE) which by its nature, incidence, severity or outcome has not been identified in the current risk assessment. [USADE is synonymous with UADE below from the United States (US) Code of Federal Regulations (CFR)³.]

NOTE 1: Anticipated serious adverse device effect (ASADE) is an effect which by its nature, incidence, severity or outcome has been identified in the risk assessment.

Clinical Study Protocol
Johnson & Johnson Vision Care, Inc.

Unanticipated Adverse Device Effect (UADE) – A UADE is any serious adverse effect on health or safety or any life-threatening problem or death caused by, or associated with, the test article, if that effect, problem, or death was not previously identified in nature, severity, or degree of incidence in the investigational plan, Investigator's Brochure or protocol, or any other unanticipated serious problem associated with the test article that relates to the rights, safety and welfare of subjects. [UADE is synonymous with USADE above from ISO 14155¹.]

